The efficacy of extended-release (ER) levomilnacipran has been established for major depressive disorder (MDD) in doses ranging from 40 mg/day to 120 mg/day (Sambunaris et al, 2014; Asnis et al, 2013). Levomilnacipran is the most noradrenergically active of the SNRI class of antidepressant drugs. Levomilnacipran was found to have twofold greater potency for norepinephrine relative to serotonin reuptake inhibition, and 17 and 27 times higher selectivity for norepinephrine reuptake inhibition compared with venlafaxine and duloxetine, respectively (Auclair et al, 2013).

Cognitive dysfunction in MDD is common and associated with greater impairment in functioning and quality of life. Given the similarities in mechanisms of action, it is possible for levomilnacipran to have beneficial effects on neurocognition. Apathy is considered a disorder of motivation and can occur in neuropsychiatric syndromes as well as depression. It is associated with neurocognitive disturbances and functional impairment. It remains understudied in depression.

Augmentation by adjunctive atypical antipsychotics is recommended as one of the clinical strategies on par with antidepressant switch in the APA guidelines to treat MDD. Quetiapine (extended release) is an atypical antipsychotic approved as adjunct to antidepressants for treatment of MDD in doses between 150-300 mg/day and has been extensively used in clinical practice.

Needs assessment: There is a significant unmet clinical need in terms of patients with MDD who show inadequate response and remission with SSRI treatment. Scientific evidence that guides appropriate treatment strategies in terms of further steps of switching or augmentation of medications will improve clinical care in patients with MDD who do not show adequate response to SSRIs.

II. STUDY OBJECTIVE(S):

Primary:

1. To compare the efficacy and tolerability of switching to levomilnacipran ER (40-120 mg/d) versus augmentation with quetiapine 150-300 mg/day to the patients' existing treatment for patients with inadequate relief on generic SSRIs in patients with MDD.

Secondary:

1. To examine the response and remission rates following the switch from generic SSRI to levomilnacipran ER and augmentation with quetiapine.
2. To examine changes in neurocognitive and apathy measures after switching from SSRI to levomilnacipran and after augmentation with quetiapine in MDD

III. STUDY DESIGN and PLAN:

Methodology:

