This is an 8-week, randomized rater blinded parallel group, 2-arm trial to comparing a switch to levomilnacipran ER versus augmentation with quetiapine.

Participants who meet inclusion/exclusion criteria for inadequate response to existing antidepressants will be randomly assigned (1:1 ratio) to either levomilnacipran ER or augmentation with quetiapine and their existing antidepressants in the same dose for 8 weeks. A flexible dose regime of levomilnacipran ER 40-120 mg/d mg per day will be employed with titrating doses starting at 20 mg/d on Days 1-2, increasing to 40 mg/d on Days 3-7 in week 1, then flexibly dosed between 40 mg/d -120 mg/d during weeks 2 through 8. FDA approved package insert guidelines will be followed for the adjunctive

quetiapine dosing. Quetiapine will be started at 50 mg/d on Day 1-2, increasing to 150 mg/d on Days 3-7 in Week 1 and then flexibly dosed between 150-300 mg/d during Weeks 1 through 8 along with their current antidepressant. Patients who cannot tolerate the higher dose of levomilnacipran ER or quetiapine will have their dose reduced to a lower dose per the investigator's judgment. The primary efficacy measure rating will be performed by a blinded rater.

IV. STUDY POPULATION:

- A. A total of 60 subjects (n=30 in each group) will be studied at 2 sites. A total of 40 subjects will be screened for a total of 30 eligible subjects to be enrolled at Duke.
- B. Potential participants will be identified by self-referral via the printed ad, phone Script, the patients' physicians, local health providers, mental health providers, or Duke providers; if not self-referred, the potential participant will have the study introduced by a care provider known to them as meeting the inclusion criteria will be offered basic information about the protocol by the PI or Study Coordinator and if interested, provided with an appointment for the purposes of obtaining informed consent and screening assessments.

During the phone screen interview the study coordinator will collect specific protected health information (PHI) for ascertaining subject eligibility and to determine if an appointment should be set up. If the is ineligible to participate or decides not to participate in the study, the PHI will be destroyed. The PI or Study Coordinator will also clearly explain to them that a refusal to participate in the study will not affect their participation to treatment at their regular treating physician or Duke University Medical Center (DUMC).

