C. Inclusion Criteria

- Male or Female - ages 18-65 years of age inclusive
- Current diagnosis of Major Depressive Disorder based on DSM-IV criteria

- Able to understand study rules and procedures and willing to sign written informed consent for study participation
- Inadequate response to antidepressants: having a score of ≥ 14 on the 17-item HAMD and not having a $\geq 50\%$ reduction in HAMD or CGI-S scores from baseline after a retrospective confirmation of an adequate trial of a single antidepressant (defined as a minimum 6-week trial of acceptable therapeutic dose (daily dose ≥ 40 mg of fluoxetine, 40 mg of paroxetine, 20 mg of citalopram, 10 mg of escitalopram, 37.5 mg of paroxetine CR, 150 mg of sertraline, 100 mg of fluvoxamine).

If female, nonpregnant/nonlactating status

- Duration of current MDD ≥ 4 weeks and < 24 months
Not more than 2 treatment failures of adequate antidepressant trials for current episode of MDD

D. Exclusion Criteria

- Has previously participated in a levomilnacipran ER or quetiapine XR or quetiapine clinical study in previous 12 months
- Has 1 or more the following: Current or past history of: manic or hypomanic episode, schizophrenia or any other psychotic disorder defined in the DSM- 5
- Diagnosis of alcohol or other substance use disorder (except nicotine and caffeine) as defined in the DSM-5 that has not been in sustained full remission for at least 6 months prior to screening (participant must also have negative urine drug screen prior to baseline).
- Presence or history of a clinically significant neurological disorder (including epilepsy)
- Poorly controlled Hypertension or Diabetes
- uncontrolled narrow-angle glaucoma
- hypersensitivity to levomilnacipran, milnacipran , quetiapine or quetiapine XR
- Neurodegenerative disorder.
- Has a thyroid stimulating hormone value outside the normal range at the Screening Visit that is deemed clinically significant by the investigator.

- Has clinically significant abnormal vital signs as determined by the investigator.
- Has a clinical significant abnormal electrocardiogram.
- Has screening laboratory values greater than 2.5 times the upper or lower limits of normal range or judged to be clinically significant

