All allowed concomitant medications will be unchanged throughout the study. Other psychotropic medications will require a 2-4 week washout, depending on the half life of the applicable medication after the subject is deemed eligible after the screening visit. Subjects will be monitored weekly by phone for side effects or symptom worsening during the taper. Subjects randomized to the Levomilnacipran switch arm will have their SSRI tapered over 2-4 weeks after they are determined to be eligible for the study to avoid risk of discontinuation syndrome. Subjects randomized to the adjunctive quetiapine arm will have their pre-existing antidepressants continue unchanged at baseline. A flexible dose regime of levomilnacipran ER 40-120 mg/d mg per day will be followed with the FDA approved package insert. Initial titration dose will be 20 mg/d Days 1-2, increasing to 40 mg/d from Days 3-7 in week 1, flexibly dosed between 40 mg/d - 120 mg/d week 2 to week 8. FDA approved package insert guidelines will be followed for adjunctive quetiapine dosing. Adjunctive quetiapine will be started at 50 mg/d Day 1-2, increasing to 150 mg/d Days 3-7 and flexibly dosed between 150-300 mg/d week 1-8. Patients who cannot tolerate the higher dose of levomilnacipran ER or quetiapine will have their dose reduced to the lower dose per the investigator's judgment. At the end of the 8-week trial, subjects in each group will have 1-week taper of study drug. A week 9 follow up safety assessment will be performed. Subjects will be told how to safely restart their

prior medication or can be provided with a referral for continued treatment as needed.

Any new medication started during the study will be evaluated by the investigator to determine its effect on study integrity and subject safety. Subjects and primary raters will be blinded to study drug and doses.

Arm I: Levomilnacipran ER flexible dose regime (40-120 mg/d): titration dose of 20 mg po once a day from days 1-2, then 40 mg po once a day, 80mg po once a day or 120 mg once a day.

Arm II: Quetiapine flexible dose regime: 50 mg po once a day as initiating dose, 150 mg po once a day (during the period that the subjects will be titrated on 150 mg; they will be given 1-50mg tab and 1-100 mg tab with instructions to be taking once per day) (, then 300 mg po once a day.

C. Visit specific procedures and sequence:

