This is an 8-week trial with a 1 week (week 9) safety follow up visit. Visits will be planned to occur at the screening visit and weeks 0, 1, 2, 3, 4, 6, 8 and 9.

The following activities and/or assessments will be performed at/during the Screening visit (Week -4 to Week 0):

- Obtain written informed consent prior to performing any of the formal screening procedures.
- Administer the M.I.N.I
- Administer the C-SSRS, MADRS, ASEX, HAM-D, HAM-A, DSST, CGI-S, RVLTL, Spontaneous Reported AEs and Sheehan Disability
- Record demographic information
- Obtain medical and surgical and psychiatric history
- Record prior and concomitant medications
- Record vital signs (temperature, heart rate, supine and orthostatic blood pressure), body height and body weight
- Perform a complete physical examination
- Perform a 12-lead ECG

- Collect blood and urine samples for evaluation of standard laboratory safety test (chemistry, hematology, and urinalysis)
- Assess all applicable inclusion and exclusion criteria
- Schedule the baseline visit for those subjects that do not require washout of prohibited medications
- Subjects requiring washout of prohibited medication will be provided washout requirements
 - Subjects in adjunctive quetiapine arm will be permitted to continue their pre-existing antidepressants if FDA approved for depression; if not FDA approved, they will be switched to an FDA approved medication for the duration of the study but will undergo washout of other prohibited medications
- Provide instructions on washout of prohibited medication(s), including the duration of the washout period (if needed)
- Assess for and record AEs and concomitant medications

Once potential eligibility is confirmed, the investigator, or a person designated by the investigator, will contact the subject by telephone at or during the Randomization/Baseline (Week 0):

- Determine appropriate duration of the washout period of prohibited medication(s), taking into account any labeling requirements for tapering of medication dose(s), as well as the minimal washout requirements

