Using Cohen's d effect size to determine sample size, in Cohen's standard text on statistical power (Cohen, 1988), using the NICE definition of a $d=0.5$ or larger, we obtain an estimated sample size (given a two-sided $\alpha = 0.05$ and $1 - \text{Beta} = 0.800$) of $n= 30$ per arm or 60 for the study. A power analysis was also conducted based on an effect size estimate derived from the drug-placebo difference in primary outcome of MADRS scores in published levomilnacipran trials (Citrome, 2013). The summary of Least square mean change between drug and placebo at 95% CI was -4.9 ($p<.0001$). With a two-tailed $\alpha= 0.05$, a sample size of $n= 60$ provides a power of 0.80.

B. Randomization Method

Randomization will occur with randomly generated computer lists held at the Duke site. This group will assign subjects according to a computer-generated the randomization sequence (without blocking or stratification) for each site. After the study coordinator determines eligibility, the participant will be randomized to one of two different arms. Drug capsules will be placed in standard medicine bottles. Each bottle will be dispensed individually by the study coordinator at the appropriate visit. Rater unblinding will be done at the end of the study after data lock. In case of any AEs or SAEs or other emergencies that require the blind to be broken, the pharmacy will have a 24-hour on call support service.

Power analysis was performed using an internet based software program. The results showed that a sample size of $n=60$ ($n=20$ in each of the 3 groups) could detect a strong effect with $\alpha = .05$, unless the true mean difference is quite minimal.

C. Plan of Data analysis

Subjects will be defined as able to be evaluated by two methods. The primary method will be an intent-to-treat analysis, including those who discontinue drug due to lack of efficacy or due to side effects. The secondary method will be completer analysis. The intent-to-treat (ITT) group will include randomly assigned patients receiving study drug with a post baseline efficacy assessment. The safety population will comprise all patients receiving study drug with a post baseline safety assessment.

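### The visit procedures replace the background antidepressant of some quetiapine-arm patients, although the design and regimen sections keep it unchanged, so anyone affected gets a switch as well as an add-on

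*Combined protocol and SAP*

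**What the plan says.** Four parts of the protocol bear on the background antidepressant in the quetiapine arm.

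- **Objective (section II).** The comparator is "augmentation with quetiapine 150-300 mg/day to the patients' existing treatment".
- **Design (section III, Methodology).** The arm receives "augmentation with quetiapine and their existing antidepressants in the same dose for 8 weeks". No exception is given.
- **Regimens (section V.B).** "Subjects randomized to the adjunctive quetiapine arm will have their pre-existing antidepressants continue unchanged at baseline". Again no exception is given.
- **Visit procedures (section V.C, screening visit).** Quetiapine-arm patients may continue their antidepressant if it is FDA approved for depression; "if not FDA approved, they will be switched to an FDA approved medication for the duration of the study". They also wash out other prohibited medications.

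The entry criterion (section IV.C) asks for inadequate response to an adequate trial of a single antidepressant, lasting at least 6 weeks. The qualifying doses are for fluoxetine, paroxetine and "20 mg of citalopram, 10 mg of escitalopram, 37.5 mg of paroxetine CR, 150 mg of sertraline, 100 mg of fluvoxamine". Nothing there requires approval for depression.

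In the levomilnacipran arm (section V.B) the SSRI is tapered over 2 to 4 weeks and replaced by levomilnacipran. No other antidepressant is kept or substituted.

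**The concern.** A site cannot follow all of these instructions for the same patient. A drug substituted under section V.C is neither the existing antidepressant of section III nor the pre-existing one of section V.B.

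What is at stake is the meaning of the quetiapine arm. Augmentation here means adding quetiapine to a drug that has been tried and found inadequate. An affected patient instead starts two treatments close together: a new antidepressant, on which inadequate response has not been shown, and quetiapine. Improvement in that patient could not be credited to augmentation. The levomilnacipran arm has no counterpart, since its patients have one switch and no add-on.

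The rule is also awkward to run. It depends on the arm but appears among the screening activities (Week -4 to Week 0), whereas the Schedule of Events (section XIV) places randomisation at Week 0.

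**Working it through.** The plan states no figure on this point, so there is none to reproduce. The check compares the texts, works through the timing, and then illustrates the possible size.

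**1. Can the texts be read together?** The phrase in section V.B about continuing unchanged at baseline might mean unchanged from Week 0 onward, after a switch during screening. That reading fails on the word pre-existing in the same sentence, and on section III, which speaks of existing antidepressants at the same dose. If section V.C is a deliberate exception, sections III and V.B do not say so.

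**2. Exposure to the substituted drug.**

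- Switch at the start of the screening window: about 4 weeks at Week 0, and 4 + 8 = 12 weeks at Week 8.
- Switch only once the arm is known at Week 0: 0 weeks at Week 0, and 0 + 8 = 8 weeks at Week 8.

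In both cases exposure at Week 0 is shorter than the 6 weeks that section IV.C requires of an adequate trial, so the new drug may still be taking effect while the outcome is measured. The first case has a further difficulty: if the switch comes before randomisation, the site does not yet know which patients the rule covers.

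**3. Possible size.** From the documents: 30 patients per arm (section IV.A) and the planning statement "Least square mean change between drug and placebo at 95% CI was -4.9" (Statistical Evaluation, part A). Assumed, because the documents do not give them: the number affected k, the extra change per affected patient delta (either sign), and the SD of MADRS change.

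Shift in the quetiapine-arm mean = k × delta / 30.

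| k | delta (points) | Shift (points) | Share of 4.9 |
|---|---|---|---|
| 0 | 4 | 0 | 0% |
| 1 | 4 | 4/30 = 0.13 | 2.7% |
| 3 | 4 | 12/30 = 0.40 | 8.2% |
| 6 (deliberately high) | 5 | 30/30 = 1.0 | 20.4% |

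The assumed SD runs from 8 to 12. A value of 4.9 / 0.5 = 9.8 follows if the plan's d of 0.5 and its 4.9 points describe the same effect, which the plan does not say. Standard error of the difference = SD × √(2/30).

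| SD | Standard error | 0.4 / SE | 1.0 / SE |
|---|---|---|---|
| 8 | 2.07 | 0.19 | 0.48 |
| 9.8 | 2.53 | 0.16 | 0.40 |
| 12 | 3.10 | 0.13 | 0.32 |

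The 4.9 points are a drug-placebo difference. They serve only as a yardstick and are not the effect expected between these two arms.

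**The case against.** The strongest reply is that nobody may be affected. Section IV.C limits the qualifying drug to named products, and the documents do not say that any of them lacks approval for depression. This stands, and it limits the point to a conditional one. A reader might infer that some listed product is unapproved and that patients will therefore be switched; the documents do not support that step.

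Second, a switch made because of the assigned arm is part of the assigned strategy, and the analysis keeps such patients where they were randomised: "The intent-to-treat (ITT) group will include randomly assigned patients receiving study drug with a post baseline efficacy assessment". That is right, and the randomised comparison of strategies remains valid. It does not restore the contrast the objective names, because the strategy would then be a switch plus an add-on for these patients.

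Third, MADRS is measured again at Week 0, and baseline MADRS is a covariate. Any effect of an early switch that had appeared by Week 0 is therefore in the baseline score. This helps in part, but it does nothing about an effect that emerges afterwards.

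Fourth, section V.B provides a check: "Any new medication started during the study will be evaluated by the investigator to determine its effect on study integrity and subject safety". This is a case-by-case judgement and sets no rule for the conflict.

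Finally, one could simply cross-refer to the exception in sections III and V.B. That would cure the inconsistency of wording but leave the mixed treatment in place.

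**Conclusion.** The conflict between section V.C and sections III and V.B is real, and the rule as written gives any affected patient a treatment that is not augmentation of existing therapy. The correction is minor. The number affected is unknown and may be zero, the sign of any effect is unknown, and the size is probably small: 0.13 to 0.19 standard errors for 3 patients, and under half a standard error even in the deliberately high case. These figures rest on assumed values of k, delta and SD.

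Two stronger readings should be resisted. A reader might infer that the primary result is biased towards quetiapine; the documents give neither a number affected nor a direction. A reader might also infer a breach of the entry criteria; there is none, because the patient qualified on the earlier drug.

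**What to change.** In section V.C, delete the clause that switches the antidepressant, and keep the washout of other prohibited medications. In section IV.C, require of every patient, before randomisation, that the qualifying antidepressant is FDA approved for depression. Check the listed products against that requirement and remove any that fails it. The same rule then applies to both arms and does not depend on knowing the assignment, and sections III and V.B can stand as written.

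The cost is one clause removed, one inclusion line added and one check of the list, with no new data collection. The downside is that a few patients, or one listed product, may become ineligible. No sensitivity analysis is needed: with the clause gone there is no group to examine, and one this small could hardly change a conclusion.

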 - Weekly phone calls will include a Symptom Checklist, consistent with symptoms of Major Depression, suicidal risk and adverse events, which the Study Coordinator will review with the subject. Any potential concerns will be reviewed with the subject. Any potential concerns will be discussed with the PI and appropriate interventions for subject safety will be planned. The same symptom checklist and monitoring plan for the subjects will be used at the Duke and the non-Duke site.
- Assess all applicable inclusion and exclusion criteria

- Administer the C-SSRS, MADRS, ASEX, HAM-A, DSST, CGI-S, RVLTL, AES, Spontaneous Reported AEs and Sheehan Disability
- Assess for and record AEs and concomitant medications
- Dispense study medication

The following activities and/or assessments will be performed at Weeks 1 through Weeks 6:

- Assess for and record AEs and concomitant medications
- Administer the C-SSRS, MADRS, ASEX, HAM-A, DSST, CGI-S, RVLTL, AES, Spontaneous Reported AEs and Sheehan Disability
- Collect study medication and review medication compliance
- Dispense study medication

The following activities and/or assessments will be performed at Week 8: End of Study or Early Termination:

- Assess for and record AEs and concomitant medications
- Collect study medication and review medication compliance
- Record vital signs (temperature, heart rate, supine and orthostatic blood pressure), and body weight
- Collect blood and urine samples for evaluation of standard laboratory safety tests
- Administer the C-SSRS, MADRS, ASEX, HAM-A, DSST, CGI-S, RVLTL, AES, Spontaneous Reported AEs and Sheehan Disability
- Perform a 12-lead ECG

The following activities and/or assessments will be performed at the Week 9/ Safety Follow-Up Visit:

- Assess for and record AEs and concomitant medications
- Administer the C-SSRS, Spontaneous Reported AEs and the DSST

After all study assessments has been completed or if the participant completes an early term visit, the participants will be referred back to their outpatient treating physician for

psychiatric care. Participants who are uninsured will be referred to Lincoln Community Health Center or Durham Access. Results of the subject's participation will not be available to the subject before they return to their treating doctor.

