Patient termination will occur if the patient experiences a clinically significant worsening of MADRS scores in two successive visits or any worsening on CSSRS on two consecutive visits, or based on clinician judgment or patient preference.

D. Concomitant Medications and Therapy:

All medications for pre-existing medical conditions will be permitted to continue unchanged provided subjects are on a stable dose of at least 12 weeks. Subjects on prohibited concomitant mood stabilizers or atypical antipsychotics will require a 2-4-week washout of the prohibited medication after the subject meets all eligibility criteria at the screening visit. Washout of prohibited medication will be determined by the $\frac{1}{2}$ life of the drug. Subjects on a minimum of 3 months of stable dose of hypnotics (e.g. zolpidem 10 mg per day or benzodiazepine dose of ≤ 2 mg per day of lorazepam or trazodone ≤ 100 mg per day) will be allowed to continue their hypnotic medication at the same dose. Over the counter medications will be permitted if in the opinion of the investigator, they are not considered to have any significant impact on the study. Any medication that has the potential to cause a clinical significant drug interaction with levomilnacipran ER or quetiapine in the judgment of the investigator will require a washout.

VI. STUDY MEDICATION

A. Description and Dispensing

a. Description and Dispensing

Levomilnacipran and quetiapine will be dispensed/administered at specified study visits.

b. Storage

All study medications will be stored in a double-locked cabinet in the Civitan Building. With available access only to the study investigator and research coordinator.

VII. CLINICAL ASSESSMENTS

Diagnostic Evaluation: The Mini-International Neuropsychiatric Interview (MINI) (version 6.6) for DSM-5 Axis I Disorders to establish diagnosis.

Study Parameters/Efficacy:

Efficacy:

The primary outcome measure will be:

Change from Baseline to end of treatment in Montgomery-Åsberg Depression Rating Scale (MADRS) Total Score.

Secondary outcome will be:

Change from baseline to end of treatment in
Clinical Global Impression Scale- Severity (CGI-S) and Improvement (CGI-I) scores
Hamilton Anxiety Rating Scale (HAM-A) scores
Hamilton Depression Rating Scale (HAM-D) scores
Sheehan Disability Scale (SDS) total score.
Scores on Digit symbol substitution test (DSST)
Scores on Rey's Verbal Learning Test (RVLT).
Scores on Apathy Evaluation Scale (AES).

Safety/Tolerability:

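### The visit text omits CGI-I, the Schedule of Events omits AES, and both leave HAM-D at screening only, so stated secondary outcomes may not be collected or computed as defined

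*Combined protocol and SAP*

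**What the plan says.** Section II (Study Objectives) includes this secondary objective: "To examine changes in neurocognitive and apathy measures after switching from SSRI to levomilnacipran and after augmentation with quetiapine in MDD". Section VII (Clinical Assessments) lists the secondary outcomes as changes from baseline to end of treatment. Among them are "Clinical Global Impression Scale- Severity (CGI-S) and Improvement (CGI-I) scores", HAM-D and AES. Section VII.C (Plan of Data analysis) applies repeated measures ANOVA or ANCOVA to change from baseline for the secondary measures.

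Two places say what is collected and when.

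- **Section V.C, visit text.** At screening: "Administer the C-SSRS, MADRS, ASEX, HAM-D, HAM-A, DSST, CGI-S, RVLTL, Spontaneous Reported AEs and Sheehan Disability". At Week 0, at Weeks 1 to 6 and at Week 8 or early termination, in identical words: "Administer the C-SSRS, MADRS, ASEX, HAM-A, DSST, CGI-S, RVLTL, AES, Spontaneous Reported AEs and Sheehan Disability". AES enters only in the closing part of these later lists, "RVLTL, AES, Spontaneous Reported AEs and Sheehan Disability".
- **Section XIV, Schedule of Events.** One row covers CGI-I and CGI-S together and is marked at every visit from screening to Week 8. HAM-D is marked at screening only. There is no AES row.

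**The concern.** The two lists are the working instructions for the sites, and they contradict each other on two stated secondary outcomes. A coordinator who uses the table as a checklist has no prompt for AES, and one who follows the visit text has none for CGI-I. No clause says which list prevails. Ratings that were not taken cannot be recovered at analysis, and AES is the only scale that addresses the apathy part of the secondary objective.

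Two further problems come to light when the lists are compared with the outcome definitions. HAM-D has no assessment after screening in either list. CGI-I is marked before treatment starts and is to be analysed as a change from baseline, although it already expresses change.

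**Working it through.** No sample size, power or alpha figure bears on this point. The check sets the eight secondary scales against the two lists. RVLTL in the visit text is taken to be the RVLT of the outcome list.

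| Scale | Visit text: Week 0 and Week 8 | Schedule: Week 0 and Week 8 |
|---|---|---|
| CGI-S | yes | yes |
| CGI-I | no (at no visit) | yes (row shared with CGI-S) |
| HAM-A | yes | yes |
| HAM-D | no (screening only) | no (screening only) |
| SDS | yes | yes |
| DSST | yes | yes |
| RVLT | yes | yes |
| AES | yes | no (no row) |

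Counts of scales with both a Week 0 and a Week 8 assessment:

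- Visit text alone: 8 − 2 = 6 (CGI-I and HAM-D fail).
- Schedule alone: 8 − 2 = 6 (AES and HAM-D fail).
- Both lists followed together: 8 − 1 = 7 (HAM-D still fails).
- Supported by both lists independently: 8 − 3 = 5.

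**Scale of a loss, if one list is used.** Section IV gives 60 subjects at two sites, 30 of them at Duke. If one site with 30 subjects worked from the Schedule only, AES would exist for 60 − 30 = 30 subjects, about 30 / 2 = 15 per arm under 1:1 allocation. If both sites did so, there would be no AES data. The same arithmetic applies to CGI-I if the visit text is the list used.

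**HAM-D.** Even if the screening score were accepted as baseline, no later value exists to subtract it from. Carrying the last observation forward does not help, because there is no post-baseline HAM-D observation to carry.

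**CGI-I.** The Schedule marks the combined CGI row at screening and Week 0, before there is any treatment period over which improvement could be rated. Subtracting such a score from the Week 8 score gives a quantity with no clear meaning. The rating at end of treatment is already the change measure.

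**The case against.** Sites are bound by the whole protocol. Section VII names both CGI-I and AES, and a site that combined the two lists would collect both. The monthly teleconferences between sites are to cover assessment scales and efficacy measures, which makes an unnoticed total loss less likely. This stands: loss of an outcome in full is a worst case, not the expected result. It does not remove the contradiction, and it does nothing for HAM-D, which neither list schedules after screening.

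The Schedule was read from a PDF, so a lost AES row cannot be fully excluded. The other scale rows are intact, however, and the lists differ elsewhere too: DSST at Week 9 is in the visit text only, and the Week 8 physical examination is in the Schedule only. That pattern suggests two lists that were never reconciled.

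The early marks in the shared CGI row may be meant for CGI-S alone, since the visit text names only CGI-S at screening and Week 0. That is a fair reading of the row. The definition of CGI-I as a change from baseline remains a problem either way.

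A reader might also infer that AES needs a screening value, and that a baseline taken after the SSRI taper in the switch arm biases the apathy comparison. The documents do not support this. Week 0 is the plan's baseline visit, the visit text gives AES there, and no analysis uses a screening score. A post-taper baseline, if it occurred, would affect every scale and not AES in particular. Nor is the sequence settled: section V.B describes tapering subjects already randomised to the switch arm, while the Schedule places randomisation at Week 0.

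**Conclusion.** The inconsistency is real and should be corrected. Under either list taken alone, two of the eight secondary outcomes cannot be computed as defined. With both lists combined, one still cannot, and that one is HAM-D. CGI-I is in addition specified in a form that does not suit the scale. The primary outcome is not affected, because MADRS is in both lists at every visit from screening to Week 8.

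The conclusion assumes that the Schedule as read is complete. The loss of AES or CGI-I further depends on a site working from one list only. The documents do not show that any site would do so, and they do not support reading the loss as certain. The HAM-D and CGI-I definition points do not depend on which list is used.

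**What to change.** - **AES:** add a row to the Schedule at Weeks 0, 1, 2, 3, 4, 6 and 8, to match the visit text. No screening assessment is needed.
- **CGI-I:** add it to the visit text for Weeks 1 to 8. Split the combined Schedule row so that only CGI-S is marked at screening and Week 0. In sections VII and VII.C, compare arms on the Week 8 (end-of-treatment) CGI-I score instead of a change from baseline.
- **HAM-D:** add it at Week 0 and Week 8 in both lists, or remove it from the secondary outcomes and keep it as a screening measure only.

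The cost is small. AES and CGI-I need document edits only, since each is already intended in one of the two lists. Keeping HAM-D means two more administrations per participant of a scale already in use, at most 2 × 60 = 120 in the trial. Removing it costs nothing in data collection.
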